30] Aloe Vera also inhibits the cyclooxygenase pathway, dropping the production of prostaglandins, thus decreasing the inflammation. [31]

Some studies stated the use of aloe Vera in dentistry in numerous areas like disinfecting dental unit water network, [32] gutta-percha sterilization, [33] antiseptic effect on candida albicans, [34] Aphthous stomatitis management, [35] as an ingredient in toothpastes [36-37] and mouthwashes.[28] Up to date, limited studies have been reported in relation to the effect of topical application of aloe Vera in the periodontal pocket for periodontal disease management. [38]

The null hypothesis is that flurbiprofen has no statistically significant effect in comparison to Aloe Vera gel as an adjunctive to SRP in the reduction of periodontal pockets in smoking patients with chronic periodontitis stage III.

Aim of this study:

This study aims to evaluate clinically the effect of flurbiprofen gel in comparison to Aloe Vera gel as adjunctive to SRP in the reduction of periodontal pockets in patients with chronic periodontitis stage III in smoking patients.

Materials and methods:

Participants:

This study was conducted at the Department of Oral Surgical Sciences, Division of Periodontology, Faculty of dentistry, Beirut Arab University (BAU)-Lebanon after approval of Institutional Review Board (IRB) with trial NO 2022-H-0100-D-R-0487. Patients were first briefed about the study and written consent was obtained. The study was performed in compliance with the principles of the Declaration of Helsinki.

The estimated sample size will be calculated according to <http://epitools.ausvet.com.au/>, by taking the means of clinical attachment level at 3 months in both groups from a previous similar study conducted by (39) where mean for test site = 5.75 ± 0.35 and mean for control site is = 6.4 ± 0.3 , where the variance will be calculated to be 0.35, assuming a confidence level of 95% and a study power of 80%. The calculated sample size will be 14 patients per group (28 operating sites). However, as some dropouts may be expected, a minimum of 20 patients per group were recruited

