Inclusion criteria: 60 patients were selected who had clinical periodontal loss and radiographic bone loss of stage III/grade C with no history of systemic disease. They had at least 2 periodontal sites with a pocket depth of six mm or greater, radiographic evidence of bone loss extending to the middle third of the root, and clinical attachment loss of five mm or more. Eligible subjects were categorized as current smokers if they consistently smoked more than 10 cigarettes per day for a minimum of 5 years. Additionally, individuals with no record of undergoing any periodontal treatment within the six months preceding the study were considered for inclusion. These stringent criteria aimed to ensure a relevant and homogeneous patient cohort for the research investigation.

Exclusion criteria: Patients with systemic illnesses such as diabetes mellitus or conditions that could potentially impair wound healing were excluded from participation. Additionally, individuals who were pregnant or lactating were not considered for inclusion in the study. Subjects who had been prescribed systemic antibiotics or non-steroidal anti-inflammatory drugs (NSAIDs) within the three months preceding the study were also excluded. Furthermore, individuals with confirmed or suspected hypersensitivity to Flurbiprofen or aloe Vera, the focus of the investigation, were not included in the study population. These stringent exclusion criteria aimed to control for potential confounding factors and establish a well-defined and relevant patient group for the research analysis.

Clinical protocol

Initial therapy was performed on all patients and consisted of full mouth scaling and root planing on 2-4 sessions, by hand and ultrasonic instrumentation, with oral hygiene instructions reinforcement and proper brushing technique (modified Bass technique) instructions. Note that patients received the same toothbrushes, toothpaste, and interdental brushes. Oral hygiene was reinforced at every visit.

The selected patients were allocated into three groups (each containing 20) with the help of a computerized randomizer (Randomizer.org), and using a split mouth design, sites were randomly allocated for each patient into either test or control group using a coin flip method:

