Initially, the PI and GI were measured at four sites per tooth, with gingival bleeding being recorded within 15 seconds. To prevent misinterpretation of gingival bleeding as BOP, patients were asked to rinse with water after this assessment. Subsequently, all teeth were probed at six different locations per tooth. CAL was determined as the distance from the cemento-enamel junction (CEJ) to the pocket depth, while the PD was measured as the distance from the gingival margin to the base of the pocket. BOP was recorded 15 seconds after probing. It is important to note that these clinical parameters were recorded at the baseline (1st visit) before the treatment and were repeated at the fourth week (2nd visit), eighth week (3rd visit), twelfth week (fourth visit), and at 6 months (5th visit). During this observation period, participants received reinforcement of plaque control and additional instructions to maintain optimal oral hygiene

Preparation of gels:

Aloe Vera:

Aloe vera gel used in this study was 98% aloe vera[®] gel concentration (Avivir; Denmark) and 2% normal saline. Commercial preparation method of 98% concentration of aloe vera gel was washing the ripe aloe Vera leaves thoroughly under water and cutting off their skin. Each leaf was cut into several pieces and seeping gel from the pieces were collected in a sterile container and stored at 4°C until the time of application. [38]

Flurbiprofen:

Gel was made of 20% poloxamer and 10% ethanol as an Optimum formulation with sustained release up to 48 hours and a reasonable sol gel transition phase.

Statistical analysis:

Statistical analysis was done using SAS 9.4 Software (SAS Institute Inc., Cary, NC, USA). Means and standard deviations (SD) were calculated for all continuous variables (periodontal parameters: CAL, PD, BOP, GI, PI) at the baseline, fourth week, eighth week, and twelfth week and 6 months. Repeated linear mixed-effects models (PROC MIXED in SAS) were used to examine the changes in all periodontal parameters over the five-time points within each group and between groups. An unstructured covariance matrix was used, residual plots were visually reviewed to check model fit, and extreme outliers were eliminated using the restricted likelihood distance. A Tukey-Kramer 8 correction was applied to all pairwise comparisons. One-way ANOVA was used to examine group differences in PD reduction and CAL. A p-value of 0.05 was considered statistically significant.

References:

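### The unstructured five-visit mixed models name no small-sample adjustment; uncorrected, the 4-df omnibus tests would run at about 9% to 14% (group fitted alone) or 6% to 8% (pooled), not 5%

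*Combined protocol and SAP*

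**What the plan says.** All the modelling text is in one paragraph of the combined protocol and SAP, under Statistical analysis.

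- Model: "Repeated linear mixed-effects models (PROC MIXED in SAS) were used", with change across the five visits as the target, both inside each group and from one group to another.
- Covariance: "An unstructured covariance matrix was used".
- Multiplicity: a Tukey-Kramer "correction was applied to all pairwise comparisons".
- Level: "A p-value of 0.05 was considered statistically significant".

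On size, the Participants section says that "a minimum of 20 patients per group were recruited". The Clinical protocol section confirms three groups of 20, with two contralateral sites per mouth.

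The paragraph is silent on four things: the denominator-df method, any small-sample adjustment, whether each group has its own model or all 60 patients share one, and how the two sites of a mouth enter the model.

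**The concern.** An unstructured matrix for five visits has 5 × 6 / 2 = 15 parameters. A Wald F test with several numerator df uses the inverse of the estimated matrix as if it were known. With few patients the estimate is noisy, the F statistic is too large on average, and the test rejects a true null hypothesis more often than stated.

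The omnibus tests that these models supply are exposed: visit, site-treatment-by-visit and group-by-visit. G3 matters most, because it is the only group that compares flurbiprofen with Aloe Vera in the same mouth. A site-treatment-by-visit test there rests on 20 patients. Five outcomes are modelled in the same way, so any excess recurs in each.

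**Working it through.** **Inputs from the plan.** Level 0.05; five visits, so q = 4 numerator df for visit (or for site treatment by visit on within-mouth differences); 20 patients per group, 60 in all; unstructured covariance.

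**Assumptions, shown as ranges.** Complete data; no small-sample adjustment; denominator df (ddf) equal to the patient-level df ν, to 4ν, or infinite (chi-square). The plan gives none of these.

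**The plan's own figures.** It states no actual type I error beyond the nominal 0.05. Its sample size reproduces: 2 × (1.960 + 0.842)² × 0.35 / 0.65² = 13.004, rounded up to 14 per group. That 14 is used below only as a what-if for the number remaining.

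**Formula.** With complete balanced data the REML unstructured estimate equals the sample covariance on ν df, and the uncorrected F is Hotelling's T²/q. Hence

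true level = P{ F(q, ν − q + 1) > Fcrit(q, ddf) × (ν − q + 1)/ν }.

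**One group fitted alone** (ν = 20 − 1 = 19, q = 4, multiplier 16/19 = 0.842, reference F(4, 16)):

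| ddf | 5% critical value | × 0.842 | true level |
|---|---|---|---|
| 19 | 2.895 | 2.438 | 8.95% |
| 76 (4 × 19) | 2.492 | 2.099 | 12.9% |
| chi-square | 2.372 | 1.997 | 14.4% |

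**One covariance pooled over three groups** (ν = 60 − 3 = 57, multiplier 54/57 = 0.947, reference F(4, 54)):

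| ddf | 5% critical value | × 0.947 | true level |
|---|---|---|---|
| 57 | 2.534 | 2.400 | 6.1% |
| 228 (4 × 57) | 2.411 | 2.284 | 7.2% |
| chi-square | 2.372 | 2.247 | 7.6% |

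**Other multi-df tests.**
- Group by visit, 8 df, pooled covariance: simulation (40,000 runs, compound-symmetric and AR(1) correlation) gives 5.9% to 6.2% with 57 ddf and 7.8% to 8.0% with 228.
- Site difference over all five visits, 5 df: 11.3% (19 ddf) with a group fitted alone and 6.7% (57 ddf) pooled.
- If only 14 per group remained, 4 df: 11.5% (13 ddf) with a group fitted alone and 6.7% (39 ddf) pooled over 42.

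**Tests little affected.**
- A single pair of visits, 1 df, group fitted alone: the multiplier is 1, so the level is exactly 5.0% with 19 ddf. It is 6.1% with 76.
- Tukey-Kramer familywise rate over the five visits, by simulation: with a group fitted alone, 5.2% to 5.9% (19 ddf) and 7.9% to 9.0% (76 ddf). Pooled, it is 4.6% to 6.3% across 57 and 228 ddf.

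**With the correct reference.** Referring T²(ν − q + 1)/(qν) to F(q, ν − q + 1) gives 5.0% in each of the exact cases. For the 4-df test with one group alone, the critical value rises from 2.895 to 3.571; pooled over 60 patients, it rises from 2.534 to 2.684.

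**The case against.** A reader might infer that the within-group tests in this trial reject at 9% or more whatever was done. The documents do not support that, for four reasons.

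- **The 9% needs separate fits.** The plan puts within-group and between-group changes in one sentence, and comparing groups in a mixed model calls for a joint fit. Pooling is at least as natural a reading, and under it the figure is about 6% to 8%. This stands: 9% is not a lower bound.
- **Silence is not proof.** A one-paragraph summary that omits the df method does not show that no adjustment was applied. The 76-df case and the 14-patient case are also assumptions, and the plan gives no dropout rate. This stands too, and it makes the finding conditional.
- **The comparisons that the plan names are pairwise.** With patient-level df, single-df contrasts hold 5% and Tukey-Kramer visit pairs stay near 5% to 6%. The plan does not name the 4-df visit test or a site-treatment-by-visit test in G3. This limits the reach of the point, but does not remove it. Change over five visits within and between groups is what the models are meant to examine, and omnibus tests are their usual output.
- **The clinical consequence is small.** Everyone receives scaling and root planing, so no change over visits is not a null hypothesis of interest. The one-way ANOVA on PD reduction and CAL does not use the unstructured matrix. A flurbiprofen versus Aloe Vera contrast in G3 at one visit, or averaged over visits, has one df. It would therefore go too far to say that the treatment conclusions are compromised. That is why the point is minor.

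**Conclusion.** The point holds conditionally. If the models are run as described with no small-sample adjustment, the omnibus tests exceed the stated 0.05 under either reading of the plan. The 4-df test is at about 9% with a group of 20 fitted alone on 19 df (up to about 14% with larger df or a chi-square reference) and at about 6% to 8% with one covariance pooled over 60 patients. The 8-df group-by-visit test is at about 6% with 57 df.

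These figures assume complete, normally distributed data with one five-visit series per patient (one site, or the within-mouth difference). How the two sites enter also matters. If they were treated as 120 independent subjects, the 4-df visit test would be at 5.5% to 6.2%, but a split-mouth design does not guarantee that independence.

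The documents do not show that an adjustment was omitted, only that none is specified. Minor severity; a free improvement.

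**What to change.** In the Statistical analysis section:

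1. State that every mixed model uses the Kenward-Roger adjustment (DDFM=KR in PROC MIXED). It corrects both the covariance of the estimates and the denominator df, and brings the multi-df tests back to about 5% whether groups are fitted separately or jointly.
2. State that one model is fitted to all 60 patients, with group, visit and site treatment and their interactions, and take the within-group and G3 within-mouth comparisons as contrasts from it.
3. State the subject unit and how the two sites of a mouth enter the covariance. Kenward-Roger does not settle this, and it changes the error rate.

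The cost is one SAS option and a few sentences in the SAP, with no new patients or data. Omnibus tests become slightly more conservative, which is the purpose. If a small-sample method and a joint model were already used, only the sentences are needed.

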- Group one (G1): comprised of 20 patients who received treatment involving the application of flurbiprofen gel as an adjunct to scaling and root planing. Specifically, on the test site of each patient, one milliliter of 2.5% flurbiprofen gel was applied, while on the contralateral side, scaling and root planing were performed as the control intervention.
- Group two (G2): comprised of 20 patients who received treatment involving the application of aloe Vera gel as an adjunct to scaling and root planing. Specifically, on the

test site of each patient, one milliliter of 98% aloe Vera was applied, while on the contralateral side, scaling and root planing were performed as the control intervention.

- Group three (G3): The intervention involved applying flurbiprofen gel on one site, while the contralateral side received an application of 98% aloe vera.

Clinical measurements:

The clinical periodontal parameters were recorded by one blinded examiner from the mesio-buccal, mid-buccal, disto-buccal, disto-lingual, mid-lingual, and mesio-lingual surfaces of each tooth using a colour coded periodontal probe (PQWBR - Hu Friedy Mfg. Inc. Chicago, IL, USA): and checked by another blinded examiner. Examiners were calibrated to ensure intra-examiner as well as inter-examiner agreement when measuring PD and CAL values. Fifteen patients were examined twice before the trial, 24 hours apart. Calibration was considered accepted if both measurements at the baseline and after 24 hours were similar to one mm at the 90% level.

In this clinical study, various clinical measurements were undertaken to assess the oral health status of the participants. These measurements included the clinical attachment level (CAL), probing depth (PD), plaque index (PI), gingival index (GI), and bleeding on probing (BOP).

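### Data points are removed from the mixed model by an outcome-based influence measure with no cut-off or deletion unit and no stated all-data fit, so type I error can exceed 0.05

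*Combined protocol and SAP*

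**What the plan says.** The point lies in the Statistical analysis section of the combined protocol and SAP. The main model is described as follows: "Repeated linear mixed-effects models (PROC MIXED in SAS) were used to examine the changes in all periodontal parameters over the five-time points", both within and between groups. On fitting, it says "An unstructured covariance matrix was used, residual plots were visually reviewed to check model fit", and then that "extreme outliers were eliminated using the restricted likelihood distance". For multiplicity, a Tukey-Kramer "correction was applied to all pairwise comparisons", without naming the family of comparisons. A separate sentence adds that "One-way ANOVA was used to examine group differences in PD reduction and CAL", without saying whether deleted values are put back for that analysis. The level is given by "A p-value of 0.05 was considered statistically significant"; sidedness is not stated.

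Two other sections bear on this. Clinical protocol sets the design: three groups of 20 and, "using a split mouth design, sites were randomly allocated for each patient into either test or control group". Clinical measurements says that readings were "checked by another blinded examiner" and describes calibration before the trial. Neither section links measurement checking to the removal of values, and nothing elsewhere defines an outlier or plans a sensitivity analysis.

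**The concern.** Restricted likelihood distance measures how far the fit moves when part of the data is left out. It is a useful diagnostic, but here it is used to remove data. Four things needed to make that reproducible or safe are missing:

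- what counts as extreme;
- whether one reading, one site or a whole patient goes;
- a requirement that the value be a documented error;
- a fit of the same model to all data, for comparison.

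A valid value in the tail of the distribution will be flagged just as an error would be. Removing it shrinks the estimated error variance without a matching fall in the real sampling variability of the contrast. Standard errors then come out too small. If the extreme responses lie mostly on one side, the estimate moves too. With 20 patients per group, one or two patients are 5% to 10% of a group, so the choice of rule matters.

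**Working it through.** **Inputs.** From the plan: level 0.05 (two-sided assumed), 3 groups x 20 patients, two sites per patient, 5 visits. With one value per site and visit (an assumption), this is 60 x 2 x 5 = 600 values per outcome. Assumed because the plan is silent: no true effect; change from baseline to 6 months as the contrast; normal or t (4 df) data; and the deletion rules shown. Simulation error is about 0.1 percentage point unless noted.

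**Step 1: the plan's own figure.** With every value kept and normal data, the 0.05 level is reproduced: 4.96% for 20 split-mouth differences, 5.05% for flurbiprofen versus aloe vera within G3, 4.97% for test minus control in G1 versus G2, and 4.80% to 4.87% for the Tukey-Kramer families.

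**Step 2: one group, 20 paired differences at one visit.** The distance for patient i is twice the drop in the full-data restricted log-likelihood when the estimates are replaced by those obtained without i. For a mean and a variance with n = 20, it depends only on the externally studentised residual t:

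RLD = 19 ln{19/(18 + t²)} + t²(1 + 1/19) − 1

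At t = 3: 19 ln(19/27) + 9 x 20/19 − 1 = −6.68 + 9.47 − 1 = 1.80. At t = 4: −11.06 + 16.84 − 1 = 4.79. Only the outcomes enter, so the measure carries no information on whether a value is an error. Type I error of the one-sample t-test after deletion (200,000 runs):

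| Cut on t | Same cut as RLD | Normal | t (4 df) |
|---|---|---|---|
| none | – | 5.0% | 4.6% |
| 5 | 9.80 | 5.0% | 5.1% |
| 4 | 4.79 | 5.3% | 5.5% |
| 3.5 | 3.06 | 5.7% | 6.0% |
| 3 | 1.80 | 6.7% | 6.7% |
| 2.5 | 0.94 | 8.6% | 7.8% |

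A separate run (40,000) with cuts set directly on the distance, normal data, gave 6.5%, 8.5% and 11.3% at 2, 1 and 0.5, deleting on average 0.13, 0.41 and 1.02 patients.

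**Step 3: mixed model, whole patients deleted.** Unstructured covariance, REML, most influential patients removed and the model refitted (40,000 runs). Type I error in %, by number of patients deleted:

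| Contrast | 0 | 1 | 2 | 3 | 4 |
|---|---|---|---|---|---|
| Within G3, normal | 5.05 | 5.43 | 5.71 | 6.19 | 6.48 |
| G1 v G2, normal | 4.97 | 5.45 | 5.91 | 6.23 | 6.51 |
| Tukey-Kramer, six group-by-site changes, normal | 4.80 | 5.65 | 6.32 | 6.92 | 7.60 |
| Same family, random deletion | 4.80 | 4.80 | 4.88 | 4.90 | 4.81 |
| Within G3, t (4 df) | 5.01 | 5.18 | 5.25 | 5.52 | 5.64 |
| Tukey-Kramer, six changes, t (4 df) | 4.43 | 4.83 | 5.08 | 5.28 | 5.39 |
| Tukey-Kramer, three groups, one series per patient, normal | 4.87 | 6.00 | 6.89 | 7.56 | 8.34 |
| Same, t (4 df) | 4.58 | 4.98 | 5.50 | 5.90 | 6.11 |

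The random-deletion row shows that selection by outcome causes the inflation, not the loss of patients. The first six rows use both sites of all three groups, with assumed correlations of 0.6 between visits and 0.4 between sites. For normal data these do not affect the single-contrast rows.

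**Step 4: same split-mouth model, single readings deleted, normal data.** Within G3: 5.01% with all data; 5.74%, 6.75% and 8.02% after 1, 3 and 6 of 600 readings; 5.02% at a studentised cut of 4 and 5.83% at 3. Tukey-Kramer, in the same order: 4.87%; 5.76%, 7.16% and 8.92%; 4.89% and 6.00%. Here the covariance was held fixed when the distance was computed, so the distance is t²/19: cuts of 3 and 4 are 9/19 = 0.47 and 16/19 = 0.84. This scale is not the one in step 2.

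**Step 5: shift of the estimate.** In the step 2 setting, let 5% of treated sites respond 3 SD worse. Their true contribution to the mean is 0.05 x 3 = 0.15 SD. Deletion makes treatment look too good by 0.08, 0.055, 0.02 and 0.005 SD at cuts of 2.5, 3, 4 and 5. The sign reverses if they respond better. There is no shift if extremes are symmetric.

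**Step 6: an open cut-off.** If the number deleted were chosen after seeing results, counting significance at any of 0, 1, 2, 3, 4 or 6 deletions, a three-group run (4,000) gave 11.0% for one pairwise test and 12.6% familywise. This is a worst case; the plan does not say it was done.

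**The case against.** The strongest reply concerns size. The plan removes only extreme values, whereas the step 3 table removes the top one to four patients in every simulated trial, even where none is unusual. That is trimming rather than an outlier rule. Under a strict threshold the effect nearly vanishes. With a 5% Bonferroni cut over 60 patients (Mahalanobis distance as a stand-in; 20,000 runs of the split-mouth model), normal data lost a patient in 4.8% of trials and the within-G3 error went from 4.63% to 4.69%. With t (4 df) data the cut removed 3.2 patients on average and the error went from 4.95% to 5.5%. This stands: under a strict rule the harm is small, and the larger figures need a looser one. The plan, however, does not say which it used.

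It is also fair that index measures such as PI, GI and BOP are not normal or t distributed, and that the cuts in steps 2 and 4 lie on different scales. The figures show what can happen; they do not estimate what did.

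Three further replies do not rescue the clause. Checking by a second blinded examiner makes an extreme value more likely to be genuine, which weakens the case for deleting it. The one-way ANOVA may use all data, but it is named only for PD reduction and CAL and is not an all-data fit of the mixed model. Tukey-Kramer takes the post-deletion standard error as valid, so it cannot correct one that is too small. Finally, stating the cut-off and unit and reporting both fits would close the reporting gap, but would leave open which fit is the main one.

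**Conclusion.** The concern holds. The plan states an outcome-dependent deletion without the details that would make it reproducible, and applying it to valid data can push the type I error of the mixed-model comparisons above 0.05. The omission is certain; its size is not. It is nil if nothing was deleted and about 5.0% to 5.3% at strict cuts. Most looser rules examined give about 5.4% to 9%, and a low distance cut in a single group of 20 gives 11.3%. Deleting up to four whole patients from heavy-tailed data in the split-mouth model gives at most 5.6%. These figures assume no true effect, normal or t (4 df) data and the deletion rules listed. A shift in the estimate arises only if extremes are one-sided and differ between the arms compared. This should be fixed before the mixed-model p-values are relied on, but it does not by itself invalidate the trial.

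**What to change.** Replace the outlier clause in the Statistical analysis section with wording such as:

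> All recorded values are kept in the main mixed model and in the one-way ANOVA. A value is corrected or excluded only for a documented recording error, decided blind to treatment. Restricted likelihood distance is reported as a diagnostic. A refit without flagged observations, with cut-off and deletion unit stated, is a sensitivity analysis only.

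The same section should name the family of comparisons to which Tukey-Kramer applies. The section is written in the past tense, so deletions may already have been made. If so, re-analyse with all data and report the number deleted by group, site and visit.

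The cost is a change of wording and one extra model run per outcome, with no new data. The downside is slightly larger standard errors, and a real but undocumented recording error would stay in the main analysis; the sensitivity refit would show how much it matters.

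### The sample size assumes one unadjusted 5% comparison, but the analysis applies Tukey-Kramer to every pairwise comparison in an undefined family, so the stated 80% power does not describe the planned test

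*Combined protocol and SAP*

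**What the plan says.** **Sizing (Materials and methods, Participants).** The inputs are CAL at 3 months from a previous study, "mean for test site = 5.75 ± 0.35 and mean for control site is = 6.4 ± 0.3", followed by "the variance will be calculated to be 0.35". The calculation is made "assuming a confidence level of 95% and a study power of 80" per cent. The result is "The calculated sample size will be 14 patients per group (28 operating sites"). No adjustment for multiple comparisons is mentioned. Recruitment is then raised: "as some dropouts may be expected, a minimum of 20 patients per group were recruited". No dropout rate is given.

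**Design (Clinical protocol).** "The selected patients were allocated into three groups (each containing 20"), with two contralateral sites per patient in a split-mouth layout. G1 compares flurbiprofen with SRP, G2 aloe vera with SRP, and G3 flurbiprofen with aloe vera.

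**Analysis (Statistical analysis).** Mixed models cover five visits, within and between groups, for every periodontal parameter. The Tukey-Kramer "correction was applied to all pairwise comparisons". A one-way ANOVA of group differences in PD reduction and CAL is also planned. No primary contrast, primary visit or comparison family is named, and the text does not say how site enters the model.

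**The concern.** Power holds only for the test it was computed for. Here it was computed for a single contrast at the ordinary 5% critical value, while the analysis requires each contrast to pass a higher, multiplicity-adjusted value. How much higher depends on how many means are in the family, and that is left open.

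Three groups by five visits would give 15 means and 15×14/2 = 105 pairs. Many of those pairs, such as one group at week 4 against another at 6 months, do not bear on the stated aim of comparing flurbiprofen with aloe vera. Each still raises the threshold for the contrasts that do. A gel effect of the planned size could then be declared non-significant. An undefined family also leaves room to choose its width after results are seen.

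**Working it through.** **Inputs.** Difference 6.4 − 5.75 = 0.65 mm, variance 0.35, 80% power, 95% confidence, 14 calculated and 20 recruited per group (all from Participants). Two-sidedness is inferred: two-sided gives 14, one-sided gives 11.

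**Step 1: reproduce the plan's figure.** n = 2 × 0.35 × (1.960 + 0.8416)² / 0.65² = 0.70 × 7.849 / 0.4225 = 13.004, rounded up to 14. An exact t calculation gives 79.9% power at 14 (critical value 2.056, df 26) and 92.3% at 20. So 14 is the answer for one unadjusted comparison of independent means.

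**Step 2: apply the stated test.** The Tukey-Kramer critical value is q(0.95; k, df)/√2 for k means. Power comes from the noncentral t with noncentrality 0.65/√(2 × 0.35/n):
- n = 14: 0.65/√0.05 = 2.907
- n = 20: 0.65/√0.035 = 3.474

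The df are approximate: 3(n − 1), that is 39 at n = 14 and 57 at n = 20. Ranges at n = 14 cover df 39 and df 57.

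| Means in family | Critical value (df 39; df 57) | Power at 14 | Power at 20 |
|---|---|---|---|
| 3 (groups at one visit) | 2.436; 2.406 | 68–69% | 85% |
| 5 (visits within a group) | 2.859; 2.817 | 53–54% | 74% |
| 15 (groups × visits) | 3.616; 3.544 | 26–28% | 48% |

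With 3 means, power is 78% at 17 completers per group and 81% at 18. Reaching 80% needs 17–18 per group for 3 means, 22 for 5 and 30–32 for 15.

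**Step 3: within-patient correlation.** The plan gives none, so 0.5 is an assumption. It helps only contrasts made within a patient. Noncentrality becomes 0.65/√(2 × 0.35 × 0.5/n): 4.111 at 14 and 4.914 at 20. Against the same critical values, power is 95% for 3 means and 68–71% for 15 at n = 14, and 99% and 91% at n = 20.

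**Step 4: 0.35 as an SD.** The ± values are unlabelled. If they are SDs, the larger gives a variance of 0.35² = 0.1225 and a noncentrality of 0.65/√(0.245/14) = 4.914 at n = 14. With independent sites, power at 14 is 99% for 3 means and 89–91% for 15. At 20 it is 99% for 15. The pooled variance (0.35² + 0.30²)/2 = 0.106 gives slightly more.

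**Step 5: the three contrasts as designed.** Each treatment contrast lies within a different group. Taken as three paired tests at 0.05/3 = 0.0167 (variance 0.35), the critical t is 2.746 at df 13 and 2.625 at df 19. With the noncentralities above, power at 14 is 58% (correlation 0) to 89% (0.5). At 20 it is 79% to 98%.

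**The case against.** The strongest reply is that 20 per group were recruited, not 14, and that a three-group family at 20 keeps 85% power on the plan's own inputs, above the stated 80%. This stands. The qualification is that the plan presents the extra six as a dropout allowance, so 14 is the number for which power is claimed. A reader might infer that the trial as recruited is underpowered; the documents do not show that.

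A second reply is that the 15-mean family is only one reading. The plan never lists the means: correction by group (3) or by visit within group (5) is equally open, and the one-way ANOVA is itself a three-group comparison. This also stands. A reader might go further and count two sites per group at each visit, giving 30 means and 435 pairs, but nothing says that site enters the model in that way. The supportable defect is that the family is undefined, not that it is demonstrably too wide.

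Third, split-mouth pairing and the possible SD-for-variance slip both push power up, and either could remove most of the loss. Both limit the size of the problem. Neither makes the sizing rule match the test rule, and both are inputs the plan needs to settle anyway.

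Finally, over-correction is conservative. It costs power and does not raise the false-positive rate.

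**Conclusion.** The mismatch is established: the stated 80% belongs to one unadjusted comparison, and the planned test is multiplicity-adjusted. At the calculated 14 per group, with variance 0.35 and independent sites, power is below 70% even for the smallest plausible family and about a quarter for 15 means.

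At the recruited 20 the consequence is conditional. With independent sites and variance 0.35, power falls below 80% if the family has 5 or more means, or if it has 3 and completers drop to 17 per group. A within-patient correlation near 0.5 restores it for within-patient contrasts, and reading the ± values as SDs largely removes the loss throughout. It would therefore be wrong to conclude that the trial lacks its stated power under every reading. What the plan lacks is a power statement for the test it will use. The df are approximations, but the range tried moves the results by only 1–3 percentage points.

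**What to change.** 1. In Statistical analysis, restrict the multiplicity-adjusted family to three contrasts for CAL at 3 months, the endpoint used for sizing: flurbiprofen v SRP, aloe vera v SRP, and flurbiprofen v aloe vera.
2. State the estimator, because it decides the correction. If treatment means are pooled across groups in the mixed model, Tukey-Kramer over three means is suitable. Each treatment then has 40 sites at full recruitment (two groups of 20), so the powers above for 14 and 20 do not carry over. If the contrasts are three separate within-group paired comparisons, use Bonferroni or Holm, since they are not pairwise differences among three means.
3. Report other visits and cross-visit comparisons as estimates with intervals.
4. In Participants, say whether 0.35 is a variance or an SD, state an assumed within-patient correlation and a dropout rate, and restate power at the adjusted threshold for the chosen estimator.

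The cost is a few sentences, one recalculation and no extra patients. Cross-visit comparisons become descriptive, and the stated power at 14 per group may be lower. Much of the plan is written in the past tense, so the change should be dated and should say whether results had already been seen.
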